1.2.3 Drug product

Please refer to Section [4.1](#). For a more detailed description of the BI 894416 profile, please refer to the current IB [[c03536505](#)].

1.3 RATIONALE FOR PERFORMING THE TRIAL

BI 894416 is an SYK inhibitor that is being developed to be administered orally to treat patients with severe asthma.

The first single rising dose trial was conducted in healthy volunteers (1371-0001). In trial 1371-0001 doses of BI 894416 up to 70 mg were given and assessed as safe and well-tolerated.

The objective of this trial is to investigate the safety, tolerability, and pharmacokinetics of BI 894416 in healthy Japanese male subjects. The chosen population of healthy male subjects receiving single rising oral doses is considered adequate to provide the basis for the clinical development program of BI 894416 in Japan.

In this trial it is intended to investigate the safety and tolerability of 25 mg, 50 mg, and 70 mg single dose.

The dose range selected for this trial is expected to cover the potential therapeutic dose range in the further clinical development program of BI 894416.

1.4 BENEFIT - RISK ASSESSMENT

Participation in this clinical trial is without any therapeutic benefit for healthy subjects. Their participation, however, is of major importance for the development of BI 894416. Subjects are exposed to risks of trial procedures and risks related to the exposure to the trial medication.

1.4.1 Procedure-related risks

The use of an indwelling venous catheter or venepuncture for procedures such as blood sampling may result in mild bruising and, in rare cases, in transient inflammation of the wall of the vein, or in nerve injury that potentially results in paraesthesia, reduced sensibility, and/or in pain for an indefinite period.

ECG electrodes may cause local and typically transient skin reactions.

The total volume of blood withdrawn per subject during the entire trial will not exceed the volume of a normal blood donation (approximately 500 mL). No health-related risk to healthy subjects is expected from withdrawal of this volume of blood.

To ensure patient safety, all such events or symptoms reported will be managed according to the judgement of the Investigator.

1.4.2 Drug -related risks and safety measures

Potential effects on immune cells

SYK is involved in the function of basophil, mast, neutrophil and dendritic cells. Moreover, SYK is implicated in the development and function of both T cells and B cells. For details refer to the IB [[c03536505](#)].

The risk for healthy volunteers due to effects of BI 894416 on immune cells is expected to be minimal, for the following reasons:

- Inhibition of SYK is not expected to have a negative effect with regards to the immune response of innate immune cells to viral or bacterial infections, due to redundancy in the infection immune response. The key neutrophil and dendritic cell functions most likely will be triggered by alternative pathways.
- Safety and tolerability data of trial 1371-0001 are not suggestive of an increased risk of infectious adverse events, or of any relevant BI 894416-related findings in WBC, differential blood count, immunoglobulins, or lymphocyte subpopulations after single doses up to 70 mg of BI 894416 (see also IB [[c03536505](#)]).
- Due to the reversible mode of action of BI 894416 with regards to SYK inhibition, any potential effect on immune cells are expected to be of transient nature.

Risk mitigation and monitoring: Subjects with a history or diagnosis of immunological disease will be excluded from trial participation (see Section [3.3.3](#)). Adverse events will be monitored for an increase in infectious adverse events. Safety laboratory contains WBC, differential blood count, and C-Reactive Protein.

Tumour biology and carcinogenicity

The SYK pathway has been hypothesized to act as both a tumour suppressor and a tumour promoter in different types of human cancers [[R16-4459](#)]. An increased risk of carcinogenic/metastatic potential in epithelial cancers has been reported in the literature related to SYK knock-out, but not related to SYK inhibition. Allelic deletion of SYK has been associated with breast adenocarcinoma [[R15-4770](#)]. However, there is no evidence that pharmacologic inhibition of SYK will increase carcinogenicity or metastatic risk. Preclinical data with a potent and selective SYK inhibitor, BI 1002494, are in line with an absence of carcinogenic effect due to the inhibition of SYK enzymatic function [[n00243171](#)].

Risk mitigation and monitoring: Only male subjects are included in this trial and, in view that carcinogenesis is a process that develops over a long time span, single doses of BI 894416 are not considered a relevant carcinogenic risk to the male subjects participating in this trial. Accordingly, no further risk mitigation is required in this trial.

Platelet aggregation and bleeding risk

A role of SYK in platelet function has been demonstrated in literature [[R15-5470](#)]. Several platelet functions rely on SYK signalling (e.g. collagen receptor Glycoprotein VI), but others are independent of SYK [[R16-5240](#)]. *In vitro* trials using human platelets demonstrated that,

Proprietary confidential information © 2020 Boehringer Ingelheim International GmbH or one or more of its affiliated companies

at concentrations up to 100 μ M, BI 894416 had no effect on extrinsic or intrinsic coagulation pathways. Also, BI 894416 did not inhibit adenosine diphosphate-induced platelet aggregation up to 100 μ M. However, BI 894416 inhibited collagen- and arachidonic acid-induced platelet aggregation at 3 μ M and 5 μ M, respectively. However, platelet function, as measured by bleeding time, is not affected by a drug unless all the platelet pathways are inhibited, due to redundancy within the system. Therefore, no risk for bleeding exists with regard to platelet inhibition, unless a subject is also on another antiplatelet drug that blocks these other pathways. In line with this conclusion, data of previous trial 1371-0001 do not indicate any signs of an increased risk of bleeding.

Risk mitigation and monitoring: Use of any other concomitant drug that could reasonably inhibit platelet aggregation, or coagulation, such as acetylsalicylic acid, clopidogrel and warfarin, will be prohibited (see Sections [3.3.3](#) and [4.2.2.1](#)). Adverse events will be monitored for any signs of bleeding or bleeding-related adverse events.

Bone density

SYK is reported to be involved in osteoclast differentiation, development, and function. For details, see the IB [[c03536505](#)]. In this trial, each subject is treated with single doses of BI 894416. Due to the slow turnover of bone tissue, no relevant effect on bone density is expected due to single-dose administrations with BI 894416 in this trial, and no specific monitoring of bone density is necessary in this trial.

Mortality/morbidity in preclinical trials

Mortality/sacrifice due to morbidity occurred in CByB6F1 non-transgenic mice and in Wistar Han rats. Clinical signs preceding morbidity were similar in both rodent species and included respiratory changes (rapid, shallow, and/or labored breathing), decreased motor activity, ruffled fur, hunched or prostrate posture, eye changes (squinting, discharge) and/or hypothermia. One humane sacrifice due to overt neurotoxicity was done in one dog of the 3-day escalation trial. For details see the current version of the IB [[c03536505](#)].

Risk mitigation and monitoring: Data of previous trial 1371-0001 indicate good safety and tolerability of BI 894416 at all investigated doses (single oral doses up to 70 mg). The dose of BI 894416 given in this trial is equivalent to or lower than doses given previously to healthy subjects. That means, BI 894416 plasma exposures that are expected in this trial are in the range measured previously in trial 1371-0001 and that were associated with good safety and tolerability. Moreover, subjects will be in-house at the trial site, under close medical observation for 48 h after administration of BI 894416. Vital signs and ECGs will be measured during the trial, and subjects will be instructed to report AEs spontaneously and will be asked, at time points defined in the [Flow Chart](#) for AEs. In case of AEs in need of treatment, the investigator can authorize symptomatic therapy. In those cases, subjects will be treated as necessary and, if required, kept under supervision at the trial site, or transferred to another hospital, until all medical evaluation results have returned to an acceptable level.

Neurotoxicity

Proprietary confidential information © 2020 Boehringer Ingelheim International GmbH or one or more of its affiliated companies

In dog toxicology trials, acute adverse neurological effects, such as tremor and movement disorder assessed as dyskinesia (paresis/rigidity), were observed at high exposures (see IB [[c03536505](#)]). One dog was euthanized due to overt neurotoxicity in 3-day escalation trial at 90 mg/kg/day. In dose escalation trial in dogs with assessment of neurotoxicity [[n00245394](#)], all clinical signs of neurotoxicity were reversible with cessation of dosing. No structural changes were observed in histopathology. Peripheral nerve conduction velocity and electroencephalogram were unchanged. No specific mechanism causing the neurological effects in dogs has been elucidated. Therefore, it has not been determined whether the neurological changes are species specific; however, external expert review considered this is most likely a channelopathy specific to dog and not likely to occur in man (see IB [[c03536505](#)]).

Risk mitigation and monitoring: Subjects with neurological disorder or medical history of relevant neurological disorder are excluded from trial participation (see Section [3.3.3](#)). Neurological examinations, as described in Section [5.2.5.1](#), will be performed at screening, and subjects with clinically relevant findings in the neurological examination will be excluded from trial participation (see Section 3.3.3). If necessary according to the investigator, unscheduled neurological examinations may be performed at any time during the trial. Relevant findings in the neurological examination during the trial will be reported as AEs. If necessary, subjects may be sent for further, more specific evaluation and treatment to a local neurologist.

Genotoxicity, reproductive and developmental toxicity

Genetic toxicology results indicate that BI 894416 is not mutagenic or clastogenic. In the 2-week repeat dose range finding trial in male rats [[n00240179](#)], degeneration of spermatids of the testes was observed at ≥ 400 mg/kg/day, which is considered a secondary effect, related to overt toxicity and morbidity.

It is unknown whether BI 894416 or its metabolites are distributed into male semen. Therefore, there is a theoretical risk of a sub therapeutic exposure to BI 894416, or its metabolites, for a woman of child bearing potential (WOCBP) via the semen of a trial subject. Developmental and reproductive trials have not yet been conducted. Therefore, the effect of sub therapeutic concentrations of BI 894416, or its metabolites, with regards to embryofetal development has not been explored so far.

Risk mitigation: In order to address the risk of exposing an WOCBP to BI 894416, or its metabolites, via the subject's seminal fluid, subjects need to use barrier contraception (condom) or abstinence (see Section 3.3.3).

Phototoxicity

Phototoxicity potential of BI 894416 was measured in the open-lid Neutral Red Uptake test. There was no indication of phototoxicity by BI 894416. Subjects will be advised to avoid direct exposure to sun and UV light during the entire trial (see Section [4.2.2.2](#)). Further protective measures would not be necessary given the low phototoxic potential of BI 894416 (see IB [[c03536505](#)]).

Potential effects on QT interval

Preclinical trials suggested no proarrhythmic potential or cardiovascular liability with BI 894416. However, statistical results of first-in-man trial 1371-0001 suggested a dose- and concentration-dependent increase of QTcF interval. At gMean C_{max} of the 70 mg dose group, placebo- and baseline-corrected predicted mean QTcF increase was 5.9 ms (upper limit of the 90% confidence interval (CI) was 10.5 ms).

Risk mitigation: Subjects with cardiovascular disorders (Section [3.3.3](#), exclusion criterion 5), subjects who used drugs that cause QT/QTc prolongation (Section 3.3.3, exclusion criterion 11), subjects that show a marked baseline prolongation of QT/QTc interval or any other relevant ECG finding at screening (Section 3.3.3, exclusion criterion 20), and subjects with a history of additional risk factors for Torsade de Pointes arrhythmia (Section 3.3.3, exclusion criterion 21) are excluded from trial participation. Moreover, subjects will be in-house under close observation for 48 h following drug administration, and ECGs are done pre- and post-dose at the time points given in the [Flow Chart](#). Considering these risk-mitigating measures, the risks to subjects participating at trial 1371-0003 due to potential effects on QT interval are considered minimal.

Liver toxicity

Although rare, a potential for drug-induced liver injury (DILI) is under constant surveillance by the sponsor. Therefore, this trial requires timely detection, evaluation, and follow-up of laboratory alterations in selected liver laboratory parameters to ensure subjects' safety; see also Section [5.2.6.1.4](#), adverse events of special interest.

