1.2.2 Residual Effect Period

The Residual Effect Period (REP, i.e., the period after the last dose with measurable drug levels and/or with pharmacodynamic effects likely to be present) of BI 894416 has not been defined yet. However, the elimination half-life of BI 894416 is short (gMean terminal half-life between 2.96 and 5.31 h in the SRD part of trial 1371-0001) and its mode of action is reversible. This suggests that the occurrence of any potential adverse effects would likely be limited to a short time period (i.e., few days).

Conservatively, a minimum period of 14 d after last administration of BI 894416, or placebo, has been selected as the REP. Therefore, the individual subject's end of trial will be 14 d following last dosing with BI 894416, or placebo, at the earliest.

All adverse events (AE) reported between administration of trial medication and the individual subject's end of trial will be counted as on-treatment AEs.

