3.3.2 Inclusion criteria

Subjects will only be included in the trial if they meet the following criteria:

1. Healthy male subjects according to the assessment of the investigator, as based on a complete medical history, including a medical examination, vital signs (BP, PR), 12-lead ECG, and clinical laboratory tests
2. Japanese ethnicity, according to the following criteria:
 - born in Japan, have lived outside of Japan <10 years, and have parents and grandparents who are Japanese
3. Age of 20 to 45 years (inclusive) at screening
4. BMI of 18.5 to 25.0 kg/m² (inclusive) at screening
5. Signed and dated written informed consent prior to admission to the trial, in accordance with Good Clinical Practice (GCP) and local legislation

Proprietary confidential information © 2020 Boehringer Ingelheim International GmbH or one or more of its affiliated companies

6. Subjects who agree to minimize the risk of making their partner pregnant by fulfilling any of the following criteria starting from the first administration of trial medication until 90 days after last administration of trial medication

- Use of adequate contraception, any of the following methods plus condom: intrauterine device, combined oral contraceptives that started at least 2 months prior to the first drug administration.
- Vasectomized (vasectomy at least 1 year prior to enrolment)
- Surgical sterilization (including bilateral tubal occlusion, hysterectomy or bilateral oophorectomy) of the subject's female partner

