4.2.2 Restrictions

4.2.2.1 Restrictions regarding concomitant treatment

In principle, no concomitant therapy is allowed. All concomitant, or rescue therapies, will be recorded, including time of intake on trial days, on the appropriate pages of the CRF.

Acetylsalicylic acid, or other drugs that may inhibit platelet aggregation or coagulation, should be avoided during the entire trial. If necessary, acetaminophen may be given occasionally, if required to treat an adverse event require.

Drugs that may increase exposure of BI 894416 should be avoided during the entire trial. Based on in vitro data, CYP3A is involved in the metabolism of BI 894416. In addition, BI 894416 is substrate of P-glycoprotein *in vitro*. Data from the drug-drug interaction trial 1371-0004 (see Section [1.2.1](#)) indicate that inhibition of CYP3A and P-glycoprotein may cause mild increases of BI 894416 plasma concentrations. Therefore administration of CYP3A and P-glycoprotein inhibitors should be avoided during the entire trial.

BI 894416 is also a substrate of organic cation transporter 2 (OCT2). It is not excluded that inhibition of OCT2 could increase BI 894416 plasma exposure. Therefore administration of inhibitors of OCT2 should be avoided during the entire trial.

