4.2.2.2 Restrictions on diet and life style

While admitted to the trial site, the subjects will be instructed not to consume any foods or drinks other than those provided by the staff. Standardised meals will be served at the times indicated in the [Flow Chart](#). No food is allowed for at least 10 h before and 4 h after trial medication intake

One h before drug intake until 4 h after trial medication intake, fluid intake is restricted to the water administered with the trial medication, and an additional 240 mL of water served at 2 h and 4 h post-dose (mandatory for all subjects). From 4 h after drug intake on Day 1 until 24 h post-dose, fluid intake is restricted to 3 L.

Alcoholic beverages, grapefruits, Seville oranges (sour or bitter oranges), as well as their juices, dietary supplements, and products containing St. John's wort (*Hypericum perforatum*) are not permitted from 7 d before the first administration of trial medication until after the last PK sample of each trial period is collected.

Poppy seed containing products should not be consumed starting 4 d before first investigational medicinal product administration until last PK sampling of the trial.

Methylxanthine-containing drinks or foods, such as coffee, tea, cola, energy drinks, or chocolate, are not allowed from 10 h before administration of trial medication until 24 h after administration of trial medication.

Smoking is not allowed during the trial.

Excessive physical activity, such as competitive sport, should be avoided from 7 d before the first administration of trial medication until the end of trial examination.

Proprietary confidential information © 2020 Boehringer Ingelheim International GmbH or one or more of its affiliated companies

Direct exposure to the sun, or exposure to solarium radiation, should be avoided during the entire trial.

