5.2.6.2.4 Pregnancy

Once a male subject has been enrolled in the clinical trial and has taken trial medication, and if a partner of the male subject becomes pregnant, the investigator must report any drug exposure during pregnancy in this partner within 24 hours by means of Part A of the Pregnancy Monitoring Form to the sponsor's unique entry point, after a written consent of the pregnant partner.

The outcome of the pregnancy associated with the drug exposure during pregnancy must be followed up and reported to the sponsor's unique entry point on the Pregnancy Monitoring Form for Clinical Trials (Part B).

The ISF will contain the Pregnancy Monitoring Form for Clinical Trials (Part A and Part B) as well as non-trial specific information and consent for the pregnant partner.

As pregnancy itself is not to be reported as an AE, in the absence of an accompanying SAE and/or AESI, only the Pregnancy Monitoring Form for Clinical Trials and not the SAE form is to be completed. If there is an SAE and/or AESI associated with the pregnancy, an SAE form must be completed in addition

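### Minor: Protocol 1.4.2 requires condom or abstinence against seminal exposure but cites 3.3.3, which has no such rule; criterion 6 of 3.3.2 is met by vasectomy alone

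*Protocol*

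**What the plan says.** Protocol 1.4.2, under genotoxicity, reproductive and developmental toxicity, says it is not known whether BI 894416 or its metabolites reach semen and that developmental and reproductive studies have not been done. It describes a theoretical, sub-therapeutic exposure of a WOCBP partner. As mitigation it states that "subjects need to use barrier contraception (condom) or abstinence (see Section 3.3.3"). It makes no exception for vasectomy and gives no duration.

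Section 3.3.3 is the list of exclusion criteria. The contraception rule is in 3.3.2, criterion 6: "Subjects who agree to minimize the risk of making their partner pregnant by fulfilling any of the following criteria", from first administration until 90 days after the last. It offers three options:

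- an intrauterine device or combined oral contraceptive, introduced as "any of the following methods plus condom"
- "Vasectomized (vasectomy at least 1 year prior to enrolment"), with nothing about a condom
- surgical sterilisation of the female partner.

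Other behavioural measures in 1.4.2 reappear as operative restrictions. Section 4.2.2.2 has "Direct exposure to the sun, or exposure to solarium radiation, should be avoided during the entire trial", and 4.2.2.1 has "Acetylsalicylic acid, or other drugs that may inhibit platelet aggregation or coagulation, should be avoided during the entire trial".

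**The concern.** The two sections deal with different hazards. Section 1.4.2 is about drug reaching a partner through semen; criterion 6 is about conception. A condom addresses both, but vasectomy addresses only the second. Correcting the section number alone would therefore not be enough: it would send the site to a rule that a vasectomised man satisfies without the measure 1.4.2 calls for.

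Placement matters because the numbered criteria get a formal check. Protocol 8.3.1 requires documented source evidence, before allocation, that every inclusion criterion is met and no exclusion criterion applies. SAP Table 6.2: 1 has an important-deviation code (A1) for violated critical inclusion or exclusion criteria. A measure that appears only in the risk section gets neither check. At stake is a safety precaution for partners, not a trial result.

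**Working it through.** There is no plan figure to reproduce. The first step is a comparison of texts.

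| Place in Protocol | Hazard addressed | Condom or abstinence required? | Duration |
|---|---|---|---|
| 1.4.2 | Seminal exposure of a WOCBP | Yes, all subjects | None given |
| 3.3.3, criteria 1 to 27 | Not addressed | 0 of 27 criteria | – |
| 4.2.2.1 and 4.2.2.2 | Not addressed | No | – |
| 3.3.2 criterion 6, option 1 (device or pill) | Pregnancy | Condom | 90 days after last dose |
| 3.3.2 criterion 6, option 2 (vasectomy) | Pregnancy | No | 90 days after last dose |
| 3.3.2 criterion 6, option 3 (sterilised partner) | Pregnancy | No | 90 days after last dose |

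Any one option satisfies criterion 6. Option 1 delivers the condom measure. Option 3 is not in dispute, taking a surgically sterilised partner not to be a WOCBP. Option 2 is the gap: the partner may be a WOCBP and no barrier is asked for.

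The second step sizes the exposure. The inputs are the "gMean terminal half-life between 2.96 and 5.31 h in the SRD part of trial 1371-0001" (Protocol 1.2.2), the 48 h in-house stay (6.2.2), the 14-day residual effect period (REP; 1.2.2) and the 90-day window (3.3.2). Assuming first-order decline, the fraction of plasma parent drug remaining at time t is 2^(−t / half-life).

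- Discharge, longer half-life: 48 / 5.31 = 9.04 half-lives; 2^(−9.04) = 0.19%.
- Discharge, shorter half-life: 48 / 2.96 = 16.22 half-lives; 2^(−16.22) = 0.0013%.
- REP, 14 × 24 = 336 h: 336 / 5.31 = 63.3 and 336 / 2.96 = 113.5 half-lives.
- Criterion 6 window, 90 × 24 = 2160 h: 2160 / 5.31 = 406.8 and 2160 / 2.96 = 729.7 half-lives.

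These figures describe parent drug in plasma at geometric mean half-lives. The documents give no kinetics for semen or metabolites.

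Subjects on active drug: 3 groups × 6 = 18 of the 24 planned. SAP 6.1 records 6, all at 25 mg, because the trial stopped after the first group. The number who were vasectomised is not given and may be zero.

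**The case against.** The strongest reply is that 1.4.2 is itself protocol text. It covers every subject, and satisfying an entry criterion written for another purpose does not waive it. That stands. A reader might infer that a vasectomised subject can enter the trial without agreeing to the measure, or that the site works only from the criteria and restrictions. The documents support neither inference. Nothing says the site disregards 1.4.2. Consent is given after a full explanation based on a subject information form (Protocol 8.1) that is not available here and could carry the instruction. SAP code F1, for a critical safety procedure not followed, might also capture a breach if the trial team chose to use it.

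The second reply is that the route to harm is narrow. The fear is embryofetal exposure, so the partner would have to be pregnant. The vasectomy must be at least a year old, which rules out a pregnancy fathered before it and leaves vasectomy failure or conception by another route. The drug would also have to pass into semen after a single dose. This stands too and keeps the point minor. The pregnancy-reporting rule in 5.2.6.2.4, under which "the investigator must report any drug exposure during pregnancy in this partner within 24 hours", is a weaker defence because it acts after exposure.

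Two further inferences should be resisted. Criterion 6 does not list abstinence, but a narrower list of entry options puts nobody at risk, so this is not an error. Nor do the documents show that seminal exposure needs 90 days of protection. That window was written to prevent pregnancy, and it far exceeds what the plasma half-lives would suggest.

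None of this removes the mismatch. The pointer leads to a section without the rule, and the rule the site would find instead does not deliver the measure for one of its three options.

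**Conclusion.** The point holds as a minor one. Section 1.4.2 states a precaution for all subjects and cites a section that does not contain it, and criterion 6, the only related operative rule, can be met by vasectomy alone. The criteria therefore do not enforce the precaution for vasectomised subjects with a WOCBP partner. The claim goes no further than that. It does not say that such subjects went unprotected, since 1.4.2 still applies to them and the consent form is unseen.

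The practical risk is small: the exposure is theoretical and sub-therapeutic, there is one dose, and little plasma parent drug remains at discharge. That sizing assumes first-order decline and says nothing direct about semen or metabolites. No endpoint, analysis set or decision rule depends on the point. With the trial stopped after 25 mg, the correction matters mainly for the record and for any later protocol that reuses the wording.

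**What to change.** In 3.3.2 criterion 6, or as a restriction in 4.2.2.2, require condom use or abstinence for vasectomised subjects with a WOCBP partner, for a period that the sponsor states. This could be criterion 6's existing 90 days, or a shorter period with a justification specific to seminal exposure, such as the 14-day REP. In 1.4.2, change the cross-reference from 3.3.3 to whichever section then holds the rule. If the sponsor believes vasectomised men need no condom, 1.4.2 should instead say so and give the reason.

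The cost is a wording change to one criterion or restriction and to one cross-reference, with no added visit, sample or procedure. In a running trial it would need IRB/IEC and competent authority approval under Protocol 8.1.
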